5 STUDY POPULATION

There are two study populations for these research projects (a) college students and (b) CCC counselors. The inclusion and exclusion criteria for each are described below.

5.1 INCLUSION CRITERIA

College Students. We will recruit N=480 male, female, and transgender/nonbinary college students across the participating sites for the CAMPUS trial. Inclusion criteria to participate in the study consists of:

- (1) Enrolled at the university.
- (2) Eligible to receive counseling services either in person or remotely at the campus CCC.
- (3) 18 to 25 years of age.
- (4) Moderate to severe SI over the last two weeks indicated by one or more of the following:
 - A score of ≥ 2 on the Counseling Center Assessment of Psychological Symptoms (CCAPS) question, "I have thoughts of ending my life."
 - Self-report during clinical interview at intake
 - Other intake questionnaires given as standard clinical practice at CCCs (e.g., C-SSRS)
- (5) Suicidality is a focus of treatment
- (6) Agree to video recording of all therapy and assessment sessions.

CCC Counselors

We will recruit approximately N≈24 counselor participants across all participating sites. The number of counselor participants may increase or decrease throughout the project based on turnover, but we expect to maintain approximately 24 participating counselors at a time in each of the enrollment years.

Inclusion criteria to participate in the study consists of:

1. Currently or soon to be employed as a counselor or trainee at the CCC for at least the next year;
2. Willingness to work with suicidal college students;
3. Interested in learning to implement Collaborative Assessment and Management of Suicidality (CAMS) and Dialectical Behavioral Therapy for College Counseling settings (CC-DBT);
4. Willing to attend trainings in CAMS and CC-DBT;
5. Willing to have therapy sessions video-recorded and rated for adherence to the treatment model;
6. Interested in attending weekly consultation meetings to improve the quality and adherence of study treatments; and
7. Willing to complete measures about themselves and their student participants.

5.2 EXCLUSION CRITERIA

Exclusion Criteria for Student Participants and Rationale:

1. Students who are deemed clinically inappropriate to receive services at the CCC by an intake counselor because of imminent risk, severe psychosis, or inability to remain enrolled in school (e.g., academic failure);
2. Students being unable to remain enrolled in their university long enough to go through the minimum number of sessions for Stage 1 (4 sessions);
3. Students who have received services at the CCC within the last three months (i.e., ATSSs must be based on a new treatment episode).

Exclusion Criteria for Counselor Participants:

Counselors will be excluded if they don't meet inclusion criteria or do not consent to study participation after recruitment.

5.3 SCREEN FAILURES

Due to the focus of the study, potential participants will have access to the CCC no matter if they are receiving treatment through participation in the study or not. Screen failures, and/or student participants who decide that they would no longer be able to participate in the study, will continue to have access to the CCC for services.

5.4 STRATEGIES FOR RECRUITMENT AND RETENTION

Recruitment and Retention Strategies for Student Participants

Across participating sites, we will recruit a total of 480 student participants for the CAMPUS Trial. Recruitment will take place over 2 years.

Gender. In terms of gender, female students are more likely to seek treatment than male students. This is the case based on data collected at each of the participating sites and in terms of national data for treatment-seeking students.² Therefore, based on site and national data, we are predicting across sites that 60% of participants will be female, 38% will be male, and 2% will be transgender/non-binary. Two important caveats apply here: 1) Although, in general populations, females are more likely to report suicidal ideation than males, that discrepancy appears to not exist among treatment-seeking college students.²¹ Therefore, the estimated gender breakdown will stay the same even among suicidal treatment-seeking college students and this matches our experience in other suicide-focused intervention studies. 2) Currently, approximately 1.6% of treatment-seeking college students nationwide self-identify as transgender or non-binary.²¹ The NIH planned inclusion table does not allow these categories to be entered until the demographic data are in hand. So, it's not going to be reflected in the inclusion table, but it is an important demographic category given the known higher suicide rates for this segment of the population.¹⁸ These data will be collected as part of this study, reflected in recruitment reports later, and gender identity (cisgender vs. transgender/non-binary) will be explored as a moderator of treatment response in this study.

Ethnicity/Race. Across all sites, Non-Hispanic White/Caucasian students are the most common category. One site, Rutgers Newark has a higher percentage of African American/Black students (25%). One site, Duke, has a higher percentage of Asian/Asian American students (28%), and two sites (UNR and Rutgers Newark) have a higher percentage of Latinos (18% and 25%, respectively). We have averaged these percentages, and across all sites, we are predicting the following: 12% African American/Black, 1% or less American Indian/Alaska Native, 15% Asian American/Asian, 15% Hispanic/Latino/a, 1% or less Native Hawaiian or Pacific Islander, 10% Multi-racial, and 47% White/Caucasian. For the study, data will be collected on both ethnicity (Latino vs. not) and race to facilitate recruitment reports.

Inclusion of Children. No children will be included in the study. This is justified based on the setting and scientifically. The target sample for this study is college students who are between 18 and 25 years old. We set 18 as an age minimum because a) 18 is suggested as the start of “emerging adulthood”;⁵³ b) most college students are 18 and older, thus rendering our findings more generalizable; c) the proportion of college students under 18 is minimal (<5%); and d) students under 18 would need parental consent in most of the sites to participate which would impact recruitment procedures considerably as the study is currently designed.

Procedures to Monitor Enrollment and Track/Retain Participants. Recruitment and enrollment will be carefully monitored. The site PC will track participant flow through a REDCap database, from referral into the study (or not), date initial consent is scheduled, whether participant consented or not (if not, the reason(s) for refusing to participate will be documented), and dates of planned assessments, which will be shared with the IE locally, as well as the Duke Data Center (DDC). This database will be able to notify users via text or email of upcoming and over-due assessments to help facilitate participant retention.

To expedite referrals into the study for this high-risk population and minimize loss of participants, the intake counselor or study liaison will schedule an appointment with an IE directly within 24-48 hours. Participant tracking logs will be reviewed weekly locally by each site and by the cross-site SC to monitor recruitment and diversity of the sample. Files will be maintained by the DDC, with access granted to relevant individuals across sites.

Strategies to Ensure a Diverse, Representative Sample. As noted above, demographics will be tallied and tracked weekly with an eye towards ensuring that the study sample includes a representative sample of women and minorities (see Inclusion of Women and Minorities for more detail). Only students who are 18-25 years of age will participate (see Inclusion of Children). Inclusion of women (and men) and minorities was not a problem during the pilot and other studies conducted at the other sites. However, recruitment reports comparing the study sample to the population of other treatment-seeking students at that site will be discussed weekly during the cross-site SC call and reviewed every six months by the DSMB. If a significant discrepancy emerges, this will be discussed, investigated further, and corrective measures implemented, as advised.

Table 4. Assessment Reimbursement Amount by Visit for CAMPUS Trial						
	Assessment Point					
Type	Baseline	Mid Stage 1	End of Stage 1	Mid Stage 2	End of Stage 2	3-Month Follow Up
Visit Reimbursement	\$40	\$20	\$40	\$20	\$50	\$50

Participant Incentives. Participants will be reimbursed for completing study assessments at baseline (\$40), mid-Stage 1 (\$20), Stage 1 post (\$40), mid-Stage 2 (\$20), Stage 2 post (\$50), and 3-month F/U (\$50). Unless noted otherwise, the timeframe for assessments will fit the study design: “last month” for all assessment points, also “lifetime” and “last 6 months” at baseline, and “last 3 months” at F/U. The maximum total reimbursement for any student participant who completes all assessments as scheduled is \$220 (see Table 4 above).

Recruitment and Retention Strategies for Counselor Participants

This study will recruit approximately 24 counselor participants across the participating sites. Additional counselors will be recruited during the second year of the study to replace counselors who left during the first year, if needed. Recruitment will take place at the beginning of the study, prior to student participant enrollment.

Gender/Race/Ethnicity. Counselor participants will be initially identified by the CCC Director and referred to the site investigators for possible study participation. The racial, ethnic, and gender breakdown of the counselor participants are expected to reflect the diversity of the overall CCC staff.

Procedures to Monitor Enrollment and Track/Retain Participants. We will conduct an annual check-in with all counselor participants to review their experiences with the study and to determine whether they will continue participating as a study counselor for an additional year. To ensure that we maintain an adequate number of counselor participants, we will ask all counselor participants to notify the study team at least four months in advance if they are considering ending their participation. This will allow adequate time to identify and train replacement counselors.

Strategies to Ensure a Diverse, Representative Sample. N/A

Participant Incentives. Counselor participants will receive ongoing consultation and as-needed individual supervision.

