Notes (2): \$For all assessments collected as part of an Independent Evaluator (IE) visit (i.e., those assessments not collected specifically at treatment visits), there will be a +/-1 week window around the scheduled assessment date for purposes of data collection. IE assessments collected outside of this window will still be collected and values will be imputed based on when the assessment should have occurred.																
Notes (3): *These measures are exclusively collected in the Titanium electronic medical record and will be exported at regular intervals throughout the study period.																

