4.2 OVERALL DESIGN

As shown in Figure 1 (on page 9), the proposed multisite SMART will involve randomization at two stages. At Stage 1, all student participants ($N = 480$) will be randomized to 4-6 weeks of CAMS or TAU. Beginning at session 4, the counselor will rate the student participant in terms of clinical response. Insufficient responders (e.g., non-responders) to Stage 1 will be re-randomized to one of two Stage 2 treatments for an additional 1-8 weeks: 1) CAMS (either continued or for the first time) or 2) CC-DBT.

Thus, four ATSSs are possible:

- ATS-1: Start with CAMS, if responding, enter maintenance treatment; if not, continue with CAMS;
- ATS-2: Start with CAMS, if responding, enter maintenance treatment; if not, switch to CC-DBT;
- ATS-3: Start with TAU, if responding, enter maintenance treatment; if not, switch to CAMS;
- ATS-4: Start with TAU, if responding, enter maintenance treatment; if not, switch to CC-DBT.

Our pilot showed at Stage 1, 48% and 44% treatment response rates across CAMS and TAU, with 27% and 17% attrition rates, respectively—differences not statistically significant. Based on these findings, we assume an equal response rate of 50% across both Stage 1 treatments (CAMS and TAU), leaving $N=240$ participants eligible for Stage 2 treatments. Treatment responders at the end of Stage 1 will end study treatment and enter maintenance, which includes monthly monitoring and continued assessments with the IEs. All student participants will complete weekly measures as part of treatment. Research assessments by independent evaluators (IEs) will be conducted at baseline, mid-Stage 1 (Week 3), end of Stage 1 (Week 6), mid-Stage 2 (Week 10), end of Stage 2 (Week 14), and at 3-month follow-up (Week 26).

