6.1.4 RANDOMIZATION

Following the completion of the baseline assessment, the site PC will review the consent, document the randomization block variables (gender, medication, past suicide attempt), obtain randomization assignment from the Data Center at Duke University, and reveal randomization results to an already assigned counselor. Note that student participants will learn of their treatment assignment by the counselor at their first treatment visit (this procedure was used in the pilot project and received very favorably by students and counselors).

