8.3.4 TIME PERIOD AND FREQUENCY FOR EVENT ASSESSMENT AND FOLLOW-UP

The occurrence of an adverse event (AE) or serious adverse event (SAE) may come to the attention of study personnel during study visits and interviews of a participant presenting for care, or upon review by a study monitor.

As indicated in 8.4.1, AEs will be captured on the appropriate case report form (CRF). Information to be collected includes date and time the study team became aware of the event, event description, time of onset, study team's assessment of severity, relationship to study procedures, expectedness, time of resolution/stabilization of the event. AEs, as indicated in 8.4.1, occurring while on study will be documented appropriately regardless of relationship and will be followed until resolved or 7 days post-last intervention for all AEs or 30 days post-last intervention for all SAEs.

Any medical or psychiatric condition that is present at the time that the participant is screened will be considered as baseline and not reported as an AE. However, if the participant's condition deteriorates at any time during the study, it will be recorded as an AE.

Changes in the severity of an AE will be documented to allow an assessment of the duration of the event at each level of severity to be performed. Documentation of onset and duration of each episode will be maintained for AEs characterized as intermittent.

The study team will record events with start dates occurring any time after informed consent is obtained until 7 days (for AEs) or 30 days (for SAEs) post-last treatment visit. At each treatment visit, study counselors will document unsolicited AE/SAEs since the last therapy session discussed during that therapy session. At each study assessment visit, IEs will inquire about and document the occurrence of AE/SAEs since the last assessment. Events will be followed for outcome information until resolution or stabilization.

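### For NSSI and suicide attempts on the SITBI, a last-month recall does not fit evaluator visits three to four weeks apart

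*Combined protocol and SAP*

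**What the plan says.** The recall rule sits in the Participant Incentives paragraph of Section 5.4: "the timeframe for assessments will fit the study design: “last month” for all assessment points". It gives way wherever another period is noted. It also adds longer look-backs: lifetime and six months at the first interview, and three months at the final one.

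Section 4.2 lists the evaluator visits during treatment: "mid-Stage 1 (Week 3), end of Stage 1 (Week 6), mid-Stage 2 (Week 10), end of Stage 2 (Week 14"). One last visit comes twelve weeks later, in week 26. The notes to Table 1 add that "there will be a +/-1 week window around the scheduled assessment date for purposes of data collection". Randomisation comes after the baseline interview (Section 6.1.4): "Following the completion of the baseline assessment, the site PC will review the consent".

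Section 8.1 gives the SSI a two-week recall and gives the SITBI none. Section 9.3.1 makes ideation the primary dependent variable. Section 9.3.2 also names NSSI and attempts as primary outcomes, and plans a composite of ideation, attempts and NSSI whose derivation is left to the analysis team.

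For safety events a different rule applies (Section 8.3.4): "IEs will inquire about and document the occurrence of AE/SAEs since the last assessment".

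**The concern.** A fixed one-month window is longer than the three-week gaps in Stage 1 and about as long as the four-week gaps in Stage 2. Three things follow for SITBI events if the stated rule is used as written. The week-3 interview picks up events from before randomisation. An event in an overlap can be reported at two visits. An event that falls in the gap left by a missed visit is not asked about at the next one.

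Pre-randomisation events cannot reflect treatment, so they pull an early between-arm difference towards no effect. Section 9.3.1 expects these behaviours to be infrequent, so each misplaced or lost event carries more weight. The documents give no rule for dating SITBI events, for removing duplicates, or for choosing between per-visit and cumulative counts. The behavioural outcomes and the composite therefore lack a defined post-randomisation interval.

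**Working it through.** The plan states no figure on this point, so there is none to reproduce. The check is interval arithmetic in days.

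**Inputs.** Visit days are 0, 21, 42, 70, 98 and 182 (Section 4.2). Recall is M days at visits up to week 14. A month is not defined, so I assume M = 30 and show 28 to 31. Recall at week 26 is three months, taken as 91 days (Section 5.4). Visits may move 7 days either way (Table 1 notes). Randomisation is taken as day 0 (Section 6.1.4). The window at visit day v runs from v − M to v.

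| Quantity | M = 28 | M = 30 | M = 31 |
|---|---|---|---|
| Week-3 window before randomisation, M − 21 | 7 (25%) | 9 (30%) | 10 (32%) |
| Overlap of weeks 3 and 6, M − 21 | 7 | 9 | 10 |
| Overlap of weeks 6 and 10, and of 10 and 14, each M − 28 | 0 | 2 | 3 |
| Days 1–98 covered twice (sum of the three overlaps) | 7 | 13 | 16 |
| Lost if week 3 is missed, 42 − M − 0 | 14 | 12 | 11 |
| Lost if week 6 is missed, 70 − M − 21 | 21 | 19 | 18 |
| Lost if week 10 is missed, 98 − M − 42 | 28 | 26 | 25 |
| Lost if week 14 is missed, 182 − 91 − 70 | 21 | 21 | 21 |

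**Effect of the visit window (M = 30).** A week-3 visit held on day 14 reaches 30 − 14 = 16 days before randomisation (53%). Held on day 28, it reaches 2 days (7%). With no visit missed, a four-week gap stretched to six weeks leaves 42 − 30 = 12 days uncovered.

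**SSI.** Its 14-day recall gives 14 − 14 = 0 pre-randomisation days even if week 3 is held a week early.

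**Week 14.** The window starts at day 98 − 30 = 68, well after Stage 1 randomisation.

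**Illustration of dilution at week 3.** Suppose the event rate is constant, equals the control rate in both arms before randomisation, and is halved in full from day 0 in one arm. The observed rate ratio is (9 × 1 + 21 × 0.5)/30 = 0.65, or (9.44 + 10.5)/30.44 = 0.66 with an average calendar month of 30.44 days. The documents give no event rates, so this is not an estimate.

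**The case against.** The case against has several parts, and much of it stands.

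- *The primary variable is untouched.* Correct. A reader might infer from the wording of Section 5.4 that every outcome is affected. The rule yields where another period is noted, and the SSI has one.
- *The main time point is untouched.* Correct for a per-visit comparison. Aim 1 is assessed at the end of 14 weeks, and the primary contrast for Aim 2 ends with Stage 2. The week-14 window holds no events from before Stage 1 randomisation. Section 9.3.2 ties the six occasions to a continuous longitudinal outcome, which points to the SSI. The same paragraph, however, lists NSSI and attempts as outcomes, and Aim 8 analyses Stage 1 on its own, so week-3 behavioural data can enter.
- *Nothing says counts are summed.* Correct. A reader might add up the windows and infer a fixed percentage inflation of 14-week totals. No section sums SITBI counts over visits, so that inference has no basis. What is certain is only that one event can appear at two visits.
- *Attempts are backed up.* Partly. Attempts with intent to die are SAEs (Section 8.3.2), asked about since the last assessment. NSSI is listed there only with hospitalisation or an ED visit. Section 8.3.4 stops recording SAEs 30 days after the last treatment visit, although Section 8.3.2 implies a longer period. Nothing says that safety records feed the endpoint.
- *A fixed window gives equal exposure at baseline and later.* This is a real advantage for change from baseline, and the fix should preserve it.
- *A manual of procedures may set the SITBI window.* Possible, but the protocol does not say so. Column positions in Table 1 could not be confirmed in the text available. The SITBI row has six marks, which agrees with the six visits in Section 4.2.

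**Conclusion.** The concern holds for SITBI NSSI and attempts, and only there. With a 30-day month, about 30% of the week-3 window lies before randomisation, weeks 3 and 6 share about 9 days, and a missed visit leaves 12 to 26 days unasked for NSSI that is not an SAE. At the four-week gaps the overlap is trivial (0 to 3 days).

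The affected analyses are the week-3 occasion in any longitudinal behavioural model (Aim 2, and Stage 1 of Aim 8) and any cumulative count or composite built from visits. The SSI analyses and a per-visit week-14 comparison are not affected. The result assumes that the Section 5.4 default governs the SITBI, that the SITBI is given at all six visits, and that a month is 28 to 31 days. The size of any dilution is unknown. It is worth correcting because the behaviours are named as primary outcomes, but it does not threaten the main ideation result.

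**What to change.** At each post-baseline visit, ask the SITBI NSSI and attempt items *since your last completed assessment*, with the calendar date shown, as evaluators already do for adverse events. Record the date of each event. In the analysis, count only events after randomisation, count each once, and use time since the last completed assessment as exposure. State whether the behavioural outcomes and the composite are per-visit or cumulative, and over which interval. Keep the last-month item at baseline and at the later visits, so that change from baseline still compares equal windows. Keep the lifetime and six-month items at baseline.

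On the nominal schedule this gives no pre-randomisation days, no overlap, and no loss after a missed visit that is followed by a completed one. A missed final visit would still lose its interval.

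The cost is a change of interview wording, a small database change, slightly longer interviews, recall periods of unequal length (handled by the exposure term), and a flag on data already collected under the one-month window. Treatment, visit schedule and sample size do not change.

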6 STUDY INTERVENTION(S) OR EXPERIMENTAL MANIPULATION(S)

6.1 STUDY INTERVENTION(S)

6.1.1 PRE-SCREENING

Potential student participants will contact the college counseling center (CCC) to set up an initial appointment to access services (remote or in person dependent on local CCC policies). The student will be scheduled for an initial session with a counselor (for this first contact, the counselor will be referred to as “intake” and “intake counselor,” respectively, henceforth).

